Patients who have been scheduled for a PNE procedure will be will be consented for the study on the day of the procedure and screened for participation prior to the procedure by phone. Participants will be randomized with a stratified block randomization scheme (with a random block size of 4, 6, and 8 participants). Randomization sequence will be generated by statistician collaboratorr. All data will be recorded in the RedCap software and be maintained in that password-protected format until analysis. Data analysis will be performed by researchers associated with the IRB for this study. De-identified data will also be sent to statistician collaborator for analysis. The trial is powered to detect a change in VAS pain score of 1.5 points or more on a 10 point scale, a value that is taken to be the minimum clinically meaningful change for the VAS instrument.^{8,9} Data on identification key will be deleted at the conclusion of this study. Patient enrollment will conclude when 34 subjects, 17 of each group, have been enrolled in the study. Sample size was determined using G*Power so that we have 80% power to detect a difference between groups of the minimum clinically meaningful effect size of 1.5 points or greater using the two-sample test at α =0.05 and an assumed standard deviation for VAS score of 1.5 points.

Inclusion criteria:

- 1. Female patients undergoing sacral neuromodulation for the management of their OAB with SMN trial with PNE without fluoroscopy.
- 2. No contraindication to the use of lidocaine patch
- 3. Age >18 years old

Exclusion criteria

- 1. Patients who are not candidates for SNM therapy
- 2. Patients with contraindication to SNM including pregnancy
- 3. Allergy to lidocaine or adhesives
- 4. Chronic pain as an indication for the PNE procedure

Study design

[figure not shown]
The study design will be a double-blind randomized control trial comparing 4% lidocaine patch placed over the sacrum 30 minutes prior to the procedure to placebo patch. Intervention and control patches will be in envelopes labeled with study number and located within the procedure area. A patch from the envelope corresponding to the patient will be placed by a medical assistant or co-investigator who is not associated with the PNE placement procedure 30 minutes prior to the procedure start. Number of voids and incontinence episodes per day

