Patients will be called prior to their procedure to assess if they are interested in participation in this study. If they are interested, they will present with sufficient time prior to their procedure

to review and sign their consent form and have their patch (lidocaine vs placebo) placed (in place for 30 minutes). Consent form is otherwise attached.

Research Procedures

Please see study design/methodology section for further details. In addition all members of the research team will be educated on the study protocol at a division meeting or meeting set up for training purposes. All members of the research team will be able to ask questions at this education session and after the education session to ensure they are comfortable with all aspects of the study protocol. Members of the research staff that will be using REDCap (Research Electronic Data Capture) will be trained on how to use this database.

Minimizing Risks

Potential risk of breach of confidentiality will be mitigated by the redcap software and use of password protected University of Louisville computers for data entry and analysis. No one other than study investigators will be able to access data and it will be deleted at the conclusion of the study. Patient will be assigned a study number during the consent process and it will be associated with a patient identifier in REDCAP. No other location will have this information.

As this study is minimal risk there will not be oversight of the data. As this drug is available over the counter and is not investigational, it will be placed in envelopes at the start of the study and dispensed by investigators and clinic staff. All expected adverse events are of mild severity.

For this study, the following standard adverse event (AE) definitions are used:

- Adverse event: Any unfavorable and unintended sign, symptom, or disease temporally
 associated with the use of a medical treatment or procedure, regardless of whether it is
 considered related to the medical treatment or procedure.
- Serious Adverse Event (SAE): Any AE related to the study drug that results in any of the following circumstances: death, life-threatening, event requiring inpatient hospitalization or prolongation of existing hospitalization, persistent or significant disability/incapacity

AEs are graded according to the following scale:

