- Mild: An experience that is transient and requires no special treatment or intervention. The experience does not generally interfere with usual daily activities.
- Moderate: An experience that is alleviated with simple therapeutic treatments. The experience impacts usual daily activities.
- Severe: An experience that require therapeutic intervention. The experience interrupts
 usual daily activities. If hospitalization (or prolongation of hospitalization) is required for
 treatment of something related to the study drug, it becomes a SAE.

The study uses the follow AE attribution scale:

- Not related: The AE is clearly not related to the study procedure (i.e., another cause of the event is most plausible and/or a clinically plausible temporal sequence is inconsistent with the onset of the event).
- Possibly related: An event that follows a reasonable temporal sequence from the initiation of study procedures, but that could readily have been produced by a number of other factors.
- Related: The AE is clearly related to the study procedures.

Expectedness of Adverse Events:

- Uncommon: discomfort over the area the lidocaine patch was placed and discomfort with the PNE procedure itself
- Rare: Allergy to adhesive bandage or lidocaine, lidocaine toxicity

Plan for Analysis of Results

Summary statistics for demographics, procedures variables, and outcome measures will be summarized for each treatment group (lidocaine patch and control patch) using means, standard deviations, counts and proportions, as appropriate. Differences in these variables will be assessed using the two-sample t-test for continuous variables and the Fisher exact test for categorical variables. A two-sample t-test will be used to assess differences in the primary outcome of change in VAS score after procedure between groups. Differences in secondary outcomes will be considered using the two-sample t-test for continuous variables and the Fisher exact test for categorical variables. Transformations and/or non-parametric methods will be used if continuous data are found to substantially violate the assumption of approximate normality. Multivariate linear/logistic regression models may be used to assess the impact of other variables onto primary or secondary outcomes. Throughout, a significance level of α =0.05 will be used, and all tests will be two-sided. Data analysis will be performed by a biostatistician collaborator using the R statistical software.

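### The plan rules out oversight of the data and ties its adverse-event classes to no reviewer, report or pause decision; its SAE definition also leaves out serious events caused by the PNE procedure.

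*Combined protocol and SAP*

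**What the plan says.** Minimizing Risks gives the rule and its reason in one sentence: "As this study is minimal risk there will not be oversight of the data". The same section then sets up four ways of classifying an event.

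- Seriousness: "Serious Adverse Event (SAE): Any AE related to the study drug that results in any of the following circumstances", followed by the usual list of outcomes.
- Severity: mild, moderate or severe. The severe grade adds that if hospitalization is needed for "treatment of something related to the study drug, it becomes a SAE".
- Attribution: three levels, the highest being "Related: The AE is clearly related to the study procedures".
- Expectedness: an uncommon list and a rare list, the latter reading "Rare: Allergy to adhesive bandage or lidocaine, lidocaine toxicity".

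The text then moves directly to Plan for Analysis of Results. On the end of enrolment, Study Design/Methodology says: "Patient enrollment will conclude when 34 subjects, 17 of each group, have been enrolled in the study". Adverse events are to be recorded at the 1-week visit. The IRB is mentioned in connection with the researchers who analyse the data and for approving amendments that add personnel. It is not mentioned for safety reports.

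**The concern.** A classification of adverse events is useful only if each class leads somewhere: someone reads the event, someone is told, and someone decides whether to carry on. Here the only stated consequence of any class is another label, since a severe drug-related event needing hospitalization becomes an SAE. Because the plan says outright that there will be no oversight, a site cannot assume that an unwritten review is intended.

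Two things are at stake. First, patients are recruited from more than one location, and nobody is assigned to look across them, so a pattern of related reactions could go unrecognised while envelopes are still being dispensed. Second, because seriousness is made conditional on relation to the drug, some serious events would never enter the SAE category at all.

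**Working it through.** **1. Where 34 comes from.** Inputs from Study Design/Methodology: difference 1.5 points, SD 1.5 points, power 80%, α = 0.05. Plan for Analysis of Results makes the tests two-sided.

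- Standardised difference: d = 1.5 / 1.5 = 1.0.
- Normal approximation: n = 2 × (1.960 + 0.842)² / 1.0² = 15.7, so 16 per group.
- Two-sample t-test (noncentral t): n = 16.71, so 17 per group and 34 in total. Power is 0.807 at 17 per group and 0.781 at 16.

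The plan's figure is reproduced. It is a target for power on the VAS score and contains no safety element.

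**2. What each class leads to.**

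| Class | Stated consequence | Reviewer, report or pause decision |
|---|---|---|
| SAE | none | none stated |
| Mild, moderate | none | none stated |
| Severe | becomes an SAE if drug-related and hospitalized | none stated |
| Attribution level | none | none stated |
| Uncommon or rare | none | none stated |

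Adverse events are also absent from the listed outcomes and are not named in Plan for Analysis of Results.

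**3. Seriousness against attribution.** The SAE definition requires relation to the study *drug*. The attribution scale asks about relation to the study *procedures*. Take a hospitalization caused by the PNE procedure and not by the patch. On the attribution scale it can be rated related. Under the SAE definition it fails the first condition, so it is not an SAE. The sentence in the severe grade carries the same condition and does not bring it back in.

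**4. Exposure after a first event.** With 17 per group, an event in the first active-patch participant leaves 17 − 1 = 16 further active patches. If that participant is also the first enrolled, 34 − 1 = 33 further participants remain.

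**5. Illustration with assumed event rates.** The documents give no rate, so these are assumptions. The chance of at least one event among n participants is 1 − (1 − p)ⁿ.

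| Assumed rate p | n = 17 | n = 34 |
|---|---|---|
| 1% | 15.7% | 28.9% |
| 2% | 29.1% | 49.7% |
| 5% | 58.2% | 82.5% |
| 10% | 83.3% | 97.2% |

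With no events at all, the one-sided 95% upper bound on the rate is 1 − 0.05^(1/n): 16.2% for n = 17 and 8.4% for n = 34. A clean final table would therefore say little about uncommon harm. In a trial this small, most of the safety information comes from reading individual events when they happen.

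**The case against.** The strongest reply is that the sentence means only that no independent monitoring board is planned. That is reasonable for 34 participants and an over-the-counter patch. Grading and attributing an event already require someone to assess it, investigators have access to the database, treating staff would see an acute reaction, and the IRB may impose reporting duties outside this document. Most of this stands. It rules out several stronger readings that a reader might be tempted to make.

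- *Enrolment would run to 34 whatever happened.* The plan does not say so. It is silent on pausing, and the sentence about 34 belongs to the sample-size text.
- *Events would stay unseen until the final analysis.* The sentence that might suggest this, "All data will be recorded in the RedCap software and be maintained in that password-protected format until analysis", describes secure storage and not an embargo.
- *Nobody will look at the data.* Classifying events implies some assessment. What is missing is who does it, when, and what follows.
- *Staff could not learn the assignment.* Study design says "Intervention and control patches will be in envelopes labeled with study number and located within the procedure area", and no unblinding procedure is described. However, Research Materials, Records, and Privacy lists the randomization assignment among the database fields, and investigators can access the database. A lookup may be possible, though the plan does not say when the field is filled in or who may see it. Every participant also receives injected lidocaine, so some lidocaine exposure is known in both arms.

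The reply does not supply a named reviewer, a reporting route or a pause decision. Nor does the appeal to minimal risk fully agree with the plan's own text: all expected events are called mild, and mild is defined as needing no special treatment, yet lidocaine allergy and toxicity are on the expected list.

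**Conclusion.** The concern holds in this form: the plan affirmatively declines oversight, attaches no reviewer, report or pause decision to its adverse-event classes, states no rule that would pause enrolment before 34, and defines SAEs so that serious events caused by the procedure fall outside. The size is a matter of exposure, at most 16 further active patches or 33 further participants after a first event. It is not an estimate of harm, because the documents give no event rate.

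The conclusion rests on the visible text. The consent form and some opening material were not available, but the safety text reads without a break from the oversight sentence to the analysis plan. Institutional duties may exist elsewhere; the protocol does not refer to them. The missing unblinding procedure is a secondary matter of detail. This is an issue of trial conduct and safety reporting that should be corrected, and the sample size and alpha are unaffected.

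**What to change.** Replace the oversight sentence with text such as:

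> No data monitoring board is planned. The principal investigator reviews every serious event regardless of attribution, and every Severe event, allergic reaction or suspected lidocaine toxicity, on becoming aware of it, across all recruiting locations, reports it under the IRB's prompt-reporting rules, and documents whether dispensing continues.

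Remove the drug-relatedness condition from the SAE definition, and from the matching sentence in the severe grade, so that seriousness and attribution are judged separately. Without this change, review of serious events regardless of attribution would have no effect, because the definition would already have excluded the unrelated ones. Which events pause enrolment is for the investigators and the IRB to set.

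As a secondary step, describe how an assignment may be disclosed in an emergency. Any code-break should be held away from the staff who enrol patients and place patches, with each opening logged. Holding it at the point of dispensing would put future allocations within reach of people who may be co-investigators.

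The cost is one paragraph, one edited definition, a little investigator time and a few more events classed as serious. No board or extra visits are needed.

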Page **6** of **17** Version Date: prior to the PNE procedure will be recorded. A patch (intervention or control) will be removed by a medical assistant prior to provider entering the room in order to secure blinding. 1% lidocaine will be injected into the sacral procedure site for adequate pain relief. PNE procedure will then be performed. If inadequate analgesia is reported by the Patient during the procedure, additional injectable lidocaine will be administered, not to exceed 4.5 mg/kg of injectable lidocaine. The volume of injectable lidocaine used will be recorded. VAS pain scores prior to and immediately after procedure will be recorded. Patient Satisfaction Score, rate of successful PNE, rate of progression to SNS implantation, and amplitude of perineal stimulation of a Likert scale will be collected immediately after the procedure.

Patients will follow up in 1 week – as is standard of care with the PNE procedure. Adverse events such as pain or change in sensation will be recorded. Number of voids and incontinence episodes per day after the PNE procedure will be recorded. Overall satisfaction score will be recorded at that time.

In summary, overall questionnaires and data being collected include:

Figure 1: Patient flow and outcomes:

Study has been registered on Clinicaltrials.gov

Participant Recruitment Methods

Subjects will be recruited from the ULP Female Pelvic Medicine and Reconstructive Surgery (FPMRS) practice at the University of Louisville Health Care Outpatient Center (HCOC), Urogynecology Associates office at [name] and the Springs Medical Center. All Patients receiving care at University of Louisville Urogynecology who meet screening criteria will be called prior to their PNE procedure to assess for willingness to participate in this study. Women meeting study criteria will be approached by a member of the research team for consent prior to their PNE procedure. Women interested in the study will have the study explained to them, the consent reviewed, and questions addressed in a confidential manner in a private room. At the time of consent, participants will be informed that their participation in this research is voluntary and that they may discontinue participation without penalty at any time. Participants will not be reimbursed for their participation in this research study.

Informed Consent Process

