Research Materials, Records, and Privacy

Data that is to be collected with this study and entered into an encrypted database:

Demographic data

- Name
- Date of birth
- Age
- Weight
- BMI
- Race/ethnicity
- Smoking status
- Indication for PNE
- Contact information
- Randomization assignment

Page **13** of **17** Version Date:

- Study ID number
- Number of voids and incontinence episodes per day prior to the PNE procedure and 1

week after the PNE procedure

Procedural variables:

- Total amount of lidocaine used
- Side of PNE lead stimulated
- Amplitude of stimulation at completion of procedure
- VAS pain score prior to and after the PNE procedure.
- Satisfaction scale immediately post procedure and 1 week after the procedure.

1-week follow up variables:

- Adverse events of PNEs such as uncomfortable change in perineal sensation present at the 1 week post-procedure visit
- Patient satisfaction score immediately after the PNE procedure and at the 1 week postprocedure visit
- Number of days with successful stimulation
- Amplitude of stimulation at time of removal
- Bladder/ fecal diary with symptoms during the PNE trial period

3-month follow up

- Number of patients with a "successful" PNE who underwent an implantation
- Number of patients with a "successful" PNE who planned implantation but had not yet scheduled

Page **14** of **17** Version Date:

- Number of patients with a "unsuccessful" PNE who underwent staged procedure
- Number of patients with a "unsuccessful" PNE and what other treatment options they pursued in the next 3 months

Successful PNE is defined as PNE procedure which resulted in successful wire placement.

Unsuccessful PNE is defined as PNE procedure which did not result in successful wire placement.

Implantation defined as stage 2 procedure after interval PNE results showed >/=50% symptom reduction.

Staged procedure is a stage 1 procedure in the operating room as opposed to being performed as an outpatient PNE

This information will be sourced from the subjects themselves and questionnaire templates for satisfaction score and VAS pain score will be attached to this document as appendices. This information is necessary to display if the intervention results in an increased comfort with the PNE procedure or increased satisfaction with the procedure. Number of voids and incontinence episodes before and after the PNE procedure is recorded to examine if a change in procedural effectiveness occurs with this intervention.

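### No procedure-day or patch-specific adverse-event capture is specified in the visible text, so transient same-day patch reactions may be missed

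*Combined protocol and SAP*

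**What the plan says.** **When adverse events are collected.** In the Study design section, the paragraph on the 1-week visit states: "Adverse events such as pain or change in sensation will be recorded". It does not say whether this means events since the procedure or only those still present. The database list in Research Materials, Records, and Privacy has one adverse-event item, under the 1-week variables: "Adverse events of PNEs such as uncomfortable change in perineal sensation present at the 1 week post-procedure visit". The procedural variables in that list are the amount of lidocaine, the side of the lead, the stimulation amplitude, the VAS pain score and the satisfaction scale. None is an adverse event.

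**How adverse events are defined.** Minimizing Risks uses a broad definition, beginning "Any unfavorable and unintended sign, symptom, or disease temporally" and extending to anything linked in time to a treatment or procedure, whatever its cause. It also supplies a three-level severity scale and a three-level attribution scale.

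**What is expected.** The expectedness list has two lines: "Uncommon: discomfort over the area the lidocaine patch was placed and discomfort with the PNE procedure itself" and "Rare: Allergy to adhesive bandage or lidocaine, lidocaine toxicity". The same section states: "All expected adverse events are of mild severity". Its definition of the lowest grade is "An experience that is transient and requires no special treatment or intervention".

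**What is analysed.** Plan for Analysis of Results does not mention adverse events, and safety is not among the Objectives.

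**The concern.** The patch is what the trial randomises, and it is on the skin for half an hour before the procedure. Reactions to it would be expected mainly on that day. The one adverse-event item in the database list concerns the PNE rather than the patch, and is worded for events present a week later. Staff who followed that list literally would have nowhere to enter a rash seen when the patch came off, or symptoms that settled before the patient left.

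At stake is how far a statement of no observed patch-related harm could be trusted. If the expected reactions have no data item at the time they are likely to occur, a count of zero may mean either that nothing happened or that nobody was asked to write it down. The severity and attribution scales also have no matching field in the list, so a recorded event might be neither graded nor attributed.

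**Working it through.** **1. The passages side by side**

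| Question | Study design | Minimizing Risks | Research Materials, Records, and Privacy |
|---|---|---|---|
| Does the definition reach same-day events? | Not addressed | Yes, by association in time | Not addressed |
| When are events recorded? | 1-week visit | No window or collection step | 1-week visit |
| Limited to events still present? | No | No | Yes |
| Which events are named? | Pain, change in sensation | Patch-site and procedure discomfort, allergy, toxicity | PNE events, with perineal sensation as the example |
| Procedure-day adverse-event field? | None visible | None | None among five procedural variables |
| Grade and attribution? | Not addressed | Scales given | No field |

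Two things follow. Study design and the database list differ on whether a resolved event counts. Neither names a patch-site reaction, allergy or symptoms of toxicity as something to record, although Minimizing Risks expects them. A medical assistant removes the patch before the provider enters the room. That person first sees the skin afterwards, and has no stated recording task.

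**2. Timing**

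The background section gives a lidocaine patch half-life of 6 to 8 hours. One week is 7 × 24 = 168 hours.

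- 168 / 8 = 21 half-lives
- 168 / 6 = 28 half-lives

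A transient effect of the drug would be expected to be over by the visit. This does not apply to an adhesive or skin reaction, which need not follow drug elimination and could last a week.

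**3. What the sample size allows**

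The plan gives no adverse-event figure to reproduce. Its only design figure is 17 per group, based on a difference of 1.5, a standard deviation of 1.5, two-sided α of 0.05 and 80% power. The two-sample t-test calculation gives 16.7, rounded up to 17 per group, with power 80.7%. The figure is reproduced, and it serves here only as the denominator.

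The chance of at least one event in the 17 patch patients is 1 − (1 − p)^17. The rates p are assumed, because the documents give none:

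| Assumed rate p | Chance of at least one event |
|---|---|
| 0.1% | 1.7% |
| 1% | 15.7% |
| 5% | 58.2% |
| 10% | 83.3% |

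With zero events in 17 and complete capture, the one-sided 95% upper bound is 1 − 0.05^(1/17) = 16.2%.

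If only a fraction c of true events is recorded, the recorded rate is c × p. The same zero count then bounds p at 16.2% / c. For assumed values of c:

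- c = 0.75: 0.1616 / 0.75 = 21.5%
- c = 0.50: 0.1616 / 0.50 = 32.3%
- c = 0.25: 0.1616 / 0.25 = 64.6%

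The documents do not allow c to be estimated. The point is only that an already wide bound widens in proportion to what is not recorded.

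**The case against.** The strongest reply is that the plan does not rule out recording same-day events. Study design is not limited to events still present, so a patient could report a procedure-day reaction at the 1-week visit. The adverse-event definition covers such a reaction. The Study design section also introduces a summary of the data collected and a patient-flow figure, neither of which can be seen in the text available, and a same-day item could be there. All of this stands, and it is why the conclusion is that events may be missed.

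A reader might go further and infer that same-day events are almost entirely lost because the week-1 visit is the sole point of recording. The documents do not support that. VAS pain and satisfaction are taken immediately after the procedure, so procedural discomfort, one of the expected events, is partly captured that day. The gap concerns site reaction, allergy and symptoms of toxicity.

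A reader might also infer that a planned safety comparison between arms would be biased. None is planned, and with 17 per group little could be compared for events the plan calls rare. Nor is toxicity specific to the patch: both arms receive injected lidocaine, and the background describes systemic absorption from the patch as very low.

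On the severity sentence, the plan never grades allergy or toxicity individually, and a brief untreated skin reaction would meet its lowest grade. That some of these events would need treatment is a clinical inference. The reason given for having no data oversight is minimal risk, so the text does not show that the severity sentence drove that decision.

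What the reply does not supply is a visible procedure-day field, a stated collection window, or agreement between the two sections.

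**Conclusion.** The concern holds as a gap in the visible text. No procedure-day or patch-specific adverse-event capture is specified, and Study design and the database list disagree on whether a resolved event is recorded. Transient patch-site reactions, allergy or symptoms of toxicity on the day may therefore be missed.

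The size of the loss is unknown, because it depends on event rates and recall that the documents do not give. At best, zero events among 17 patch patients excludes rates above 16.2% (one-sided 95%), and incomplete recording makes that bound too optimistic. The primary VAS comparison and the sample size are unaffected.

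The conclusion assumes that the database list is followed as written and that the summary and figure not shown add no same-day item. If they do, what remains is to align the two sections.

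The severity sentence is a secondary wording point. As a statement about all expected events, it is not supported for allergy and lidocaine toxicity, but on its own it would not change what the trial does or concludes.

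**What to change.** 1. State one adverse-event window, from patch placement through the 1-week visit, and word Study design and the database list to match.
2. Add a procedure-day adverse-event item to the procedural variables, covering patch-site reaction, allergy, symptoms of lidocaine toxicity and other events. Grade and attribute each on the existing scales, and say who records it.
3. At 1 week, ask about any event since patch placement, whether or not it is still present.
4. Add to Plan for Analysis of Results a descriptive table of adverse events by arm. No test is needed.
5. Reconcile the severity sentence with the expectedness list, for example by removing it or limiting it to the discomfort events.

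The cost is a few REDCap fields, some rewording and about a minute of staff time for each of 34 patients. Sample size and treatment are unchanged.

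### The SAE definition requires the event to be related to the study drug, so a serious event judged unrelated, or attributed to the PNE, stays an AE and is not classed as an SAE

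*Combined protocol and SAP*

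**What the plan says.** The Minimizing Risks section sets out AE definitions that it describes as standard. For an AE, the event need only be temporally "associated with the use of a medical treatment or procedure, regardless of whether it is" thought to be caused by it. The SAE definition is narrower: "Any AE related to the study drug that results in any of the following circumstances". The circumstances listed are death, a life-threatening event, inpatient hospitalisation or its prolongation, and persistent or significant disability or incapacity.

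In the grading scale that follows, the Severe grade opens with "An experience that require therapeutic intervention" and sets no condition on cause. Its last sentence then says that if hospitalisation is needed for "treatment of something related to the study drug, it becomes a SAE".

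The attribution scale has three levels: Not related, Possibly related and Related. Each is worded against the study procedure or study procedures; none names the drug.

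Study drug is not defined. The same section says "As this drug is available over the counter and is not investigational, it will be placed in envelopes at the start of the study", and the Study design section says "Intervention and control patches will be in envelopes labeled with study number", so the patch is the natural reading. Participants also receive a second source of lidocaine: "1% lidocaine will be injected into the sacral procedure site for adequate pain relief".

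**The concern.** Seriousness describes the outcome of an event and relatedness describes its cause. The SAE definition merges the two, although the AE definition just above it keeps cause out. The rule as stated therefore gives the wrong class to some serious events when it is followed exactly. This is more than a missing detail.

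What is at stake is the meaning of the SAE label. Under this definition, a report of no SAEs would say only that no serious event was judged drug-related. A reader told that standard definitions were used would take it to mean that no serious event occurred.

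**Working it through.** No figure attaches to the SAE definition, so the check sets the rules side by side and applies them to cases.

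**Step 1: the rules.**
- AE: temporal association is enough; cause is irrelevant.
- Severe grade: depends on the need for treatment and the interruption of daily activities; cause is irrelevant.
- SAE: a listed outcome and relatedness to the study drug are both required.
- Hospitalisation sentence under Severe: worded as a sufficient condition (if drug-related, then SAE). On its own it excludes nothing. It repeats the limit that the SAE definition imposes, so there is one restriction, stated once and echoed once.
- Attribution: rated against study procedure(s).

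**Step 2: apply the rules to an event with one of the listed outcomes, such as hospitalisation.**

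| Event attributed to | AE? | Attribution rating | SAE as written? |
|---|---|---|---|
| Another clear cause | Yes | Not related | No |
| The PNE | Yes | Related | No |
| The injected 1% lidocaine | Yes | Related, if the injection is a study procedure | No if study drug means the patch; yes if it means lidocaine in either form |
| The lidocaine patch | Yes | Related, if patch placement is a study procedure | Yes |

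The first two rows do not depend on how study drug is read. The second shows the mismatch between scale and definition: an event can carry the highest attribution rating and still not be an SAE.

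**Step 3: look for text that rescues the excluded events.** No other section brings an unrelated or PNE-attributed serious event into the SAE category. The documents also do not say whether Possibly related is enough for SAE status, or whether a placebo patch counts as study drug.

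**Step 4: does anything else in the plan depend on this?** Plan for Analysis of Results mentions no SAE analysis, and no section attaches an action to an SAE. The sample size has no safety input. With a difference of 1.5 and an SD of 1.5 (effect size 1.5/1.5 = 1.0), two-sided α = 0.05 and 80% power, the noncentral t calculation gives 16.71, rounded up to 17 per group. That is 2 × 17 = 34, as the plan states, whichever SAE definition is used.

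**The case against.** The best case for leaving the text alone is that nothing is lost. A PNE-attributed hospitalisation is still an AE, can still be graded Severe and can still be rated for attribution; only a label is missing. No SAE count, comparison or stopping rule exists to be distorted, and the study is small and described as minimal risk. It can also be said that study procedures may well include patch placement. Participants were already scheduled for a PNE, so the patch is the main thing the study adds, and the scale may be ambiguous rather than blind to the drug.

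Most of this stands, and it is why the severity is minor. It does not rescue the definition. However study procedures is read, a serious event attributed to the PNE or to nothing in the study fails the SAE test. A label that will be read as a safety statement should mean what readers expect it to mean.

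Three stronger readings are tempting, and the documents do not support them:
- **That serious events will go unrecorded.** The data list under Research Materials, Records, and Privacy words its adverse-event item around the PNE. The Study design section, however, says that adverse events will be recorded at the 1-week visit, without limiting them to the PNE. What is collected is in any case a separate matter from how an SAE is defined.
- **That the absence of data oversight aggravates the fault.** The protocol does say "As this study is minimal risk there will not be oversight of the data", but oversight would not change what counts as an SAE.
- **That the attribution scale cannot capture a drug-related event.** Its wording does not isolate the drug, but it may include it. The supportable statement is that the terms do not match.

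**Conclusion.** The definition is wrong as written, with minor severity. A death, life-threatening event, hospitalisation or disability that is judged unrelated, or attributed to the PNE, meets the AE definition but cannot be an SAE. The effect is confined to the safety classification and to any statement about SAEs.

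The number of events affected cannot be estimated, because the documents give no event rate; it may be none in 34 participants. The conclusion rests on reading the SAE definition literally and does not depend on whether study drug means the patch alone or lidocaine in either form. That reading decides only how events attributed to the injection are classed.

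**What to change.** Make three wording changes under Minimizing Risks:

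1. In the SAE definition, delete the five-word qualifier that follows AE (*related to the study drug*), so that any AE with a listed outcome is an SAE.
2. In the hospitalisation sentence under Severe, delete the matching phrase (*of something related to the study drug*), so that hospitalisation for treatment of an AE makes it an SAE whatever its cause.
3. Keep relatedness as a separate rating on the existing three-level scale, and add one sentence stating what study procedures covers. At a minimum it should distinguish the patch from the PNE procedure, with the injected lidocaine counted as part of the PNE procedure. A finer split between patch and injected lidocaine is not needed: both are given at the sacral site close together and under blinding, so the choice between them could be arbitrary.

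The cost is an amendment in two places plus one sentence, and possibly a few more events labelled SAE. No data item, test or sample size changes.
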